8 TIMING OF STUDY PROCEDURES

Before performing any study-specific procedure or assessment, written informed consent and authorization for use of protected health information (HIPAA)²¹ in the US, must be obtained in accordance with all application policies, regulations, and laws. The planned study assessments are in [Section 7.2](#).

8.1 Pre-dosing

8.1.1 Visit 1: Screening

The following assessment(s) must be collected/Performed **within 28 days prior** (unless specified) to Day 1. Clinical and laboratory evaluations performed as part of routine standard of care do not need to be repeated if performed within the appropriate window.

- Eligibility: Assess against the inclusion and exclusion criteria
- Medical history: Relevant history including description of all prior therapies, and signs or symptoms
- Vital signs: Measurements include body temperature, blood pressure (BP), heart rate (HR), and respiratory rate (RR)
- Demography
- Height (cm)
- Weight (kg)

- Standard 12-lead ECG
- Physical exam (PE): A complete PE will include assessments of general appearance, skin (turgor, pallor, cyanosis, erythema, lesions), head (eyes, ear, nose, and throat), neck, lungs and heart (observation, palpation, percussion, auscultation), abdomen, back, lymph nodes, extremities, and neurological exam
- A urine or serum (beta-human chorionic gonadotropin [β -HCG]) pregnancy test is required for WoCBP; it is not required for postmenopausal or surgically sterilized women.
- Concomitant medications and procedures: Concomitant medications and procedures will be recorded beginning at the time of screening.

8.2 Dosing Period

Collection of concomitant medications and AEs as defined in Section 9.1.2 should occur throughout the study.

For imaging guidelines, refer to [Section 7.1.1](#).

8.2.1 Visit 2: Day 1, Dosing

8.2.1.1 Before Dosing

The following procedures will be performed **before** administration of the NH002 contrast injection on Day 1:

- Eligibility: Assess against the inclusion and exclusion criteria
- Medical history, including baseline signs and symptoms should be documented and continually reassessed throughout the study
- VS: Measurements include BP, body temperature, HR, and RR
- Weight (kg)
- Standard 12-lead ECG
- Focused PE: A focused PE will include cardiopulmonary (observation, palpation, percussion, auscultation) and skin (turgor, pallor, cyanosis, erythema, lesions) assessments.
- Both a urine and a serum (β -HCG) pregnancy test are required for WoCBP before dosing on Day 1. (Note that at screening, only a urine or serum test is necessary; before dosing on Day 1, both tests are necessary.)
- Complete blood count (CBC) to include hematocrit (HCT), hemoglobin (Hgb), white blood cell (WBC) count with differential, absolute neutrophil count (ANC), and platelet count (PLT)
- Coagulation studies: Thrombin time (TT) and activated partial thromboplastin time (aPTT)
- Metabolic panel: Metabolic panel evaluations to include sodium, potassium, chloride, calcium, magnesium, phosphorus, glucose, blood urea nitrogen (BUN), creatinine, total protein, albumin, alkaline phosphatase (ALP), ALT, AST, total bilirubin, and bicarbonate
- Cardiac troponin I
- Pulse oximetry: SpO₂
- Pretreatment AEs: Baseline events, findings, and conditions before NH002 initiation should be documented and continually reassessed throughout the study.

- Concomitant medications and procedures: Concomitant medications and procedures will continue to be recorded.

8.2.1.2 5 Minutes Before Dosing

The following procedures will be performed approximately **5 minutes before** dosing:

- Imaging should proceed as specified in [Section 7.1.1](#).
- Modified 12-lead ECG monitoring should be conducted, from 5 minutes before dosing to 10 minutes after dosing. See [Section 9.1.2.2.7](#).
- Pulse oximetry: SpO₂ should be measured and recorded, from 5 minutes before dosing to 10 minutes after dosing.
- VS: BP, body temperature, HR, and RR should be measured and recorded, from 5 minutes before dosing to 10 minutes after dosing.
- Record any AEs that may occur and any changes in concomitant medication.

8.2.1.3 Dosing

After all procedures have been performed, NH002 will be administered. Each subject will receive an assignment to 1 of the 3 NH002 dose levels (2.5 µl/kg, 5.0 µl/kg, or 10.0 µl/kg IV bolus). See [Section 7.5.1](#) for details. The following procedures will be performed after the contrast injection:

- Imaging should proceed as specified in [Section 7.1.1](#).
- Modified 12-lead ECG monitoring to continue until completion of imaging (ie, to 10-minutes after dosing). Any clinically significant ECG changes indicative of arrhythmia or S-T segment change identified after dosing from the modified 12-lead ECG monitoring will be recorded in a timely manner, and a standard 12-lead ECG will be conducted subsequently (when the first recorded ECG change occurs). The imaging will be temporarily stopped for the conditionally triggered standard 12-lead ECG examination. The results of the modified 12-lead ECG will also be included into the subject's study file as reference. See [Section 9.1.2.2.7](#).
- Pulse oximetry: SpO₂ should also be measured and recorded until completion of imaging (ie, 10 minutes after dosing).
- VS: BP, body temperature, HR, and RR should be measured and recorded until completion of imaging (ie, 10 minutes after dosing).
- Record any AEs that may occur and any changes in concomitant medication.

8.2.1.4 10 Minutes After Dosing

The following procedures will be performed approximately **10 minutes after** the contrast injection:

- VS: Measurements include BP, body temperature, HR, and RR
- Modified 12-lead ECG monitoring to continue until completion of imaging (ie, to 10-minutes post dosing); See [Section 9.1.2.2.7](#).

- Standard 12-lead ECG. Site(s) should make every effort to target the timing to be as close to the end of the modified 12-lead ECG monitoring (10 minutes after dosing) as possible.
- Pulse oximetry: SpO₂
- Imaging should proceed as specified in [Section 7.1.1](#).
- Record any AEs that have occurred since the previous visit and any changes in concomitant medication.

8.2.1.5 30 Minutes After Dosing

The following procedures will be performed approximately **30 minutes after** the contrast injection (+5 minutes):

- VS: Measurements include BP, body temperature, HR, and RR
- Standard 12-lead ECG
- Focused PE: A focused PE will include cardiopulmonary (observation, palpation, percussion, auscultation) and skin (turgor, pallor, cyanosis, erythema, lesions) assessments.
- Pulse oximetry: SpO₂
- Record any AEs that have occurred since the previous visit and any changes in concomitant medication.

Site(s) should make every effort to target the timing as possible. However, given that these procedures may be performed in different examination rooms in the study sites, a time window of +5 minutes is permitted.

8.2.1.6 60 Minutes After Dosing

The following procedures will be performed approximately **60 minutes after** the contrast injection (+5 minutes):

- VS: Measurements include BP, body temperature, HR, and RR
- Standard 12-lead ECG
- Focused PE: A focused PE will include cardiopulmonary (observation, palpation, percussion, auscultation) and skin (turgor, pallor, cyanosis, erythema, lesions) assessments.
- CBC to include HCT, Hgb, WBC count with differential, ANC, and PLT
- Coagulation studies: TT and aPTT
- Metabolic panel: Metabolic evaluations include sodium, potassium, chloride, calcium, magnesium, phosphorus, glucose, BUN, creatinine, total protein, albumin, ALP, ALT, AST, total bilirubin, and bicarbonate
- Pulse oximetry: SpO₂
- Record any AEs that have occurred since the previous visit and any changes in concomitant medication.

Site(s) should make every effort to target the timing as possible. However, given that these procedures may be performed in different examination rooms in the study sites, a time window of +5 minutes is permitted.

8.2.1.7 120 Minutes After Dosing

The following procedures will be performed approximately **120 minutes after** the contrast injection (+5 minutes):

- VS: Measurements include body temperature, BP, HR, and RR
- Focused PE: A focused PE will include cardiopulmonary (observation, palpation, percussion, auscultation) and skin (turgor, pallor, cyanosis, erythema, lesions) assessments.
- CBC to include HCT, Hgb, WBC count with differential, ANC, and PLT
- Coagulation studies: TT and aPTT
- Metabolic panel: Metabolic panel evaluations include sodium, potassium, chloride, calcium, magnesium, phosphorus, glucose, BUN, creatinine, total protein, albumin, ALP, ALT, AST, total bilirubin, and bicarbonate
- Pulse oximetry: SpO₂
- Record any AEs that have occurred since the previous visit and any changes in concomitant medication.

8.2.1.8 240 Minutes After Dosing

The following procedures will be performed approximately **240 minutes after** the contrast injection (+5 minutes):

- CBC to include HCT, Hgb, WBC count with differential, ANC, and PLT
- Coagulation studies: TT and aPTT
- Cardiac Troponin I
- Record any AEs that have occurred since the previous visit and any changes in concomitant medication.

8.3 Safety Follow-up Period

8.3.1 Day 4 (+3)

Subjects will be contacted by telephone at least 72 hours after NH002 dosing (ie, Day 4 [+3]) for a follow-up assessment of safety. An additional 3-day window is permitted for this Safety Follow-up, if site(s) have difficulty reaching the subject on Day 4. The following procedures will also be performed during the Safety Follow-up call:

- Record any AEs that have occurred since the previous visit and any changes in concomitant medication. Any AE or SAE should be followed up until resolved.

8.3.2 Day 7 (+3)

Subjects will be contacted by telephone again 7 days after the end of their treatment for another follow-up assessment of safety. An additional 3-day window is permitted for this second Safety Follow-up, if site(s) have difficulty reaching the subject on Day 7. The following procedures will be also performed during the Safety Follow-up call:

- Record any AEs that have occurred since the previous visit and any changes in concomitant medication. Any AE or SAE should be followed up until resolved.

8.4 Duration of Treatment

The duration of treatment is expected to last between 4 to 5 hours during 1 day, barring any unexpected adverse reactions.

9 EFFICACY AND SAFETY VARIABLES

The planned schedule of assessments is in [Section 7.2](#).

9.1 Efficacy and Safety Measurements Assessed

9.1.1 Efficacy Variables

9.1.1.1 Echocardiographic Imaging

Efficacy evaluations will be based on blinded central echocardiographic imaging assessments of LVO, duration of useful contrast enhancement, LVEBD, and diagnostic confidence:

- Left ventricular opacification (LVO): The degree of LVO following each injection was graded according to the following four-point rating scale: 0= none (no visible contrast within the LV cavity); 1= faint (weak or trace effect of contrast within the LV cavity); 2= moderate (some areas of the LV cavity fully opacified but without a time when the whole cavity was filled with contrast to the same high density); or 3= complete (homogeneous and high intensity effect).
- Duration of clinically useful contrast enhancement: The time between the disappearance of shadowing effect and the time when moderate or full LV enhancement and contrast enhancement are no longer adequate (useful effect ends).
- Left ventricular endothelial border delineation (LVEBD): To determine the impact of NH002 on EBD, a standard 12-segment model will be used, dividing the LV endocardium of the 4- or 2-chamber apical views into 6 segments, with 2 basal, mid- and apical segments in each view.

9.1.2 Safety Assessments

Each subject must be carefully monitored for the development of any AEs throughout the study from the signing of the ICF to at least 7 days after receipt of the study agent (ie, Day 7 Follow-up call). Safety evaluations will also be assessed and recorded at specified time points: before injection, during injection and imaging (beginning approximately 5 minutes prior to and continuing until 10 minutes after injection), and up to 7 days post-injection.

Safety parameters to be evaluated will include:

- Standard 12-lead ECGs assessed pre-injection, and at 10, 30, and 60 minutes post-injection; during imaging, a standard 12-lead ECG will be conditionally performed at the

earliest time point when any clinically significant ECG changes indicative of arrhythmia or S-T segment change are identified within 10 minutes after injection from the modified 12-lead ECG monitoring; each standard 12-lead ECG assessment will be scored as either normal or abnormal;

- Changes in VS assessed pre-injection, during injection and imaging (beginning approximately 5 minutes prior to and continuing until 10 minutes after), and at 30, 60, and 120 minutes post-injection; VS measurements will include body temperature, HR, RR, and BP;
- The following parameters will be included in the *complete* PE (at screening): General appearance, skin (turgor, pallor, cyanosis, erythema, lesions), head (including ear, eyes, nose, and throat), neck, lungs and heart (observation, palpation, percussion, auscultation), abdomen, back lymph nodes, extremities, and a neurological exam. A *focused* PE (after screening) will include cardiopulmonary (observation, palpation, percussion, auscultation) and skin (turgor, pallor, cyanosis, erythema, lesions) assessments; each PE assessment will be scored as either normal or abnormal;
- Changes in hematology and metabolic laboratory parameters taken pre-injection and 60, 120, and 240 minutes post-injection;
- TT and aPTT pre-injection and 60, 120, and 240 minutes post-injection;
- Cardiac troponin I pre-injection and 240 minutes (4 hours) post-injection;
- SpO₂ assessed pre-injection, during injection and imaging (beginning approximately 5 minutes prior to and continuing until 10 minutes after), and at 30, 60, and 120 minutes post-injection;
- The assessment of any potential adverse allergic reactions during and post-injection.

9.1.2.1 Overall Study Stopping Rules

The estimated duration of the study is contingent on safety and the number of dose levels evaluated in the dose escalation. See [Section 7.5.1.2](#) for stopping criteria for dosing. The study will be stopped in the event of any new findings that indicate a relevant deterioration of the risk-benefit relationship that would render continuation of the study unjustifiable. Study administration with NH002 will be halted and the DEC will convene to determine if the study should be terminated for any safety concerns. See [Section 9.2](#) for DEC details.

The sponsor may also end the study for administrative reasons.

Should the study be terminated prematurely, the sponsor will provide written notification to all investigators and regulatory authorities specifying the reason(s) for early termination. The investigator must inform the institutional review board (IRB)/independent ethics committees (IEC) promptly and provide the reason(s) for the termination. Previously dosed subjects will be assessed through all planned study safety visits.

9.1.2.2 Adverse Events

Adverse Event Definition

An AE is defined as any untoward medical occurrence in a clinical study subject administered a medicinal product which does not necessarily have a causal relationship with this treatment. An AE can therefore be any unfavorable and unintended sign (including an abnormal laboratory finding), symptom, or disease temporally associated with the use of a medicinal (investigational) product, whether or not it is related to the medicinal (investigational) product. This includes an exacerbation of pre-existing conditions or events, intercurrent illnesses, drug interaction or the significant worsening of the indication under investigation that is not recorded elsewhere in the CRF under specific efficacy assessments. Anticipated fluctuations of pre-existing conditions, including the disease under study, that do not represent a clinically significant exacerbation or worsening need not be considered AEs.

It is the responsibility of the investigator to document all AEs that occur during the study. Any AEs will be elicited by asking the subject a nonleading question, for example, "Have you experienced any new or changed symptoms since we last asked/since your last visit?". All AEs should be reported on the appropriate page of the CRF.

Assessment of Severity

Each AE will be assigned a category by the investigator as follows:

Mild: An AE that is easily tolerated by the subject, causes minimal discomfort,

and does not interfere with everyday activities.

Moderate: An AE that is sufficiently discomforting to interfere with normal everyday activities; intervention may be needed.

Severe: An AE that prevents normal everyday activities; treatment or other intervention usually needed.

If there is a change in severity of an AE, it must be recorded as a separate event.

Assessment of Causality

Every effort will be made by the investigator to assess the relationship of the AE, if any, to the study agent. Causality should be assessed using the categories presented in the following:

Unrelated: Clinical event with an incompatible time relationship to study agent administration, and that could be explained by underlying disease or other drugs or chemicals or is incontrovertibly not related to the study agent.

Unlikely: Clinical event whose time relationship to study agent administration makes a causal connection improbable, but that could plausibly be explained by underlying disease or other drugs or chemicals.

| | |
|----------------------|---|
| Possible: | Clinical event with a reasonable time relationship to study agent administration, but that could also be explained by concurrent disease or other drugs or chemicals. |
| Probable: | Clinical event with a reasonable time relationship to study agent administration, and is unlikely to be attributed to concurrent disease or other drugs or chemicals. |
| Very Likely/Certain: | Clinical event with plausible time relationship to study agent administration, and that cannot be explained by concurrent disease or other drugs or chemicals. |

Action Taken

The investigator will describe the action taken (with regard to the study agent and/or the subject) in the appropriate section of the CRF, as follows:

- None
- Study agent stopped
- Study agent temporarily interrupted
- Concomitant medication
- Other, specify.

Follow-up of Adverse Events

All investigators should follow up subjects with AEs until the event is resolved or until, in the opinion of the investigator, the event is stabilized or determined to be chronic. Details of AE resolution must be documented in the CRF.

Subjects should also be followed up 3 days (+3) and 7 days (+3) after receiving NH002 (ie, Day 4 and Day 7), and any AEs that occur during this time should be reported according to the procedures outlined in this section.

Documentation and Reporting of Adverse Events

All AEs should be reported and documented in accordance with the procedures outlined in this section. All AEs occurring during the study must be documented on the relevant CRF pages. The following data should be documented for each AE:

- Description of the symptom event
- Classification of 'serious' or 'not serious'
- Severity
- Date of first occurrence and date of resolution (if applicable)
- Action taken
- Causal relationship
- Outcome of event (unknown, recovered, not yet recovered, recovered with sequelae, death [with date and cause reported])

9.1.2.2.1 Serious Adverse Events

Serious Adverse Event Definition

An SAE is any untoward medical occurrence or effect that, at any dose,

- Results in death.
- Is life-threatening (an AE is life-threatening if the subject was at immediate risk of death from the event as it occurred; ie, it does not include a reaction that might have caused death if it had occurred in a more serious form).
- Requires or prolongs inpatient hospitalization. (Complications occurring during hospitalization are AEs and are SAEs if they cause prolongation of the current hospitalization. Hospitalization for elective treatment of a pre-existing nonworsening condition is not, however, considered an AE. The details of such hospitalizations must be recorded on the medical history or physical examination page of the CRF).
- Results in persistent or significant disability/incapacity. (An AE is incapacitating or disabling if it results in a substantial and/or permanent disruption of the subject's ability to carry out normal life functions).
- Results in a congenital anomaly/birth defect.

In addition, medical and scientific judgement is required to decide if prompt notification is required in situations other than those defined for SAEs above. This may include any event that the investigator regards as serious that did not strictly meet the criteria above but may have jeopardized the subject or required intervention to prevent one of the outcomes listed above, or that would suggest any significant hazard, contraindication, side effect, or precaution that may be associated with the use of the investigational product.

Reporting of Serious Adverse Events

Any SAE must be reported by the investigator if it occurs during the clinical study or within 4-7 days of receiving the study agent, whether or not the SAE is considered to be related to the investigational product. An SAE report consists of the SAE form, the AE form, and the concomitant medication form. A copy of these forms must be emailed **within 24 hours** for the attention of the product safety scientist at:

Name: [name]
Company: Trust Bio-sonics, Inc.
E-mail: [REDACTED]

The investigator should not wait to receive additional information to document fully the event before notification of a SAE, though additional information may be requested. Where applicable, information from relevant laboratory results, hospital case records, and autopsy reports should be obtained.

Instances of death, congenital abnormality, or an event that is of such clinical concern as to influence the overall assessment of safety, if brought to the attention of the investigator at any

time after cessation of study agent administration and linked by the investigator to this study, should be reported to the study monitor.

The sponsor and/or the appointed representative(s) will promptly notify all relevant investigators and the regulatory authorities of findings that could adversely affect the safety of subjects, impact on the conduct of the study, or alter the IEC/ IRB approval/favorable opinion of the study. In addition, the sponsor and/or the appointed representative(s), will expedite the reporting to all concerned investigators, to the IEC(s)/IRB(s), where required, and to the regulatory authorities of all adverse reactions that are both serious and unexpected.

Details of the procedures to be followed if a pregnancy occurs are also provided in [Section 7.4.4](#).

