5.2.1 Nonclinical studies

Nonclinical studies have been conducted to evaluate the pharmacology, toxicology, and genotoxicity of NH002 (Table 3). NH002 appears to have an acceptable safety profile to support the first-in-human study. Preliminary imaging results of the dog studies showed significant enhancement with low-dose NH002 as compared to saline. See the following figures (Figure 1 and Figure 2) for comparison. A pre-injection image in B-mode is provided for additional consideration (see Figure 3).

Figure 1: Imaging Results with Saline in Dog Contrast Mode

[figure not shown]

Figure 2: Imaging Results with NH002 in Dog (Contrast Mode)

[figure not shown]

Figure 3: Pre-injection Imaging Results in Dog (B-mode)

[figure not shown]

For more details regarding the study protocols for the nonclinical studies, refer to the current version of the Investigator's Brochure for NH002.

[figure not shown]
Table 3: Nonclinical Studies with NH002 Microbubble Injectable Suspension

| Study No. | Study Type | Strain/Species | Route/Doses | Study Outcome |
|-------------------------|------------|----------------|-------------|---------------|
| Pharmacology | | | | |
| Pharmacokinetics | | | | |

Toxicology

Other Studies (Hemolysis)

[figure not shown]

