7.5.1.2 Stopping Criteria for Dosing

All AEs will be evaluated during the successive cohorts of subjects, per dose level. Intrasubject dose escalations are not permitted.

Dose escalation will proceed successively with each cohort as described in previous sections ([Section 7.5.1.1](#)), unless any of the following criteria is/are exhibited:

- The occurrence of any SAE considered at least possibly related to study agent administration in any 1 subject who received study agent. The occurrence of such an SAE will supersede all other stopping rules.
- The occurrence of the following in 30% of subjects (within any one of the 3 dose levels):
 - moderate or severe clinically significant nonhematologic lab toxicity, including cardiac disorder(s)
 - moderate or severe clinically significant hematologic lab toxicity
 - mild, moderate, or severe clinically significant anaphylactic reaction

Supportive care is permissible at the discretion and clinical judgment of the treating investigator, until symptoms are resolved to baseline.

If any of the stopping criteria for dosing are observed, the study will be halted, and the risk to other subjects evaluated, prior to a decision as to whether to terminate the study (See also [Section 9.1.2.1](#) for overall study stopping rules).

Proceeding to the next dose level is permissible before completion of a cohort when no visible contrast effect and no safety concerns are observed in 4 subjects in a cohort. Such decision will be triggered by the sponsor in conjunction with the DEC, and as approved by the appropriate regulatory agencies.

A more conservative dose assignment, evaluation of an intermediate dose, and/or expansion of an existing dose level is permissible if such measures are needed for patient safety or for a better understanding of NH002 dose-related toxicity, and/or exposure. Such changes will be determined by the sponsor in conjunction with the DEC, and as approved by the appropriate regulatory agencies.

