7.5.1.6 Emergency Event Management

Subjects will be closely monitored by a medical team during the injection and for at least 4 hours (240 minutes) following dosing for the presence of symptoms of allergic or hypersensitivity reaction(s). Subjects who receive 4-hour monitoring after the dose on Day 1 will be encouraged to quickly report any symptoms at the time during this period. The necessary rescue material, equipment, and appropriate medications will be available in the clinic to allow rapid intervention in case of emergency.

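### The SAE definition, read literally, leaves out events that may have jeopardised the subject or needed intervention, so the 24-hour report and the one-subject halt are not expressly required for them

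*Protocol*

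**What the plan says.** Protocol 9.1.2.2.1 lists five SAE outcomes: death, a life-threatening event, inpatient hospitalisation or its prolongation, persistent or significant disability, and congenital anomaly. The life-threatening item is narrow: "it does not include a reaction that might have caused death if it had occurred in a more serious form".

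A separate paragraph follows the list. It says that "medical and scientific judgement is required to decide if prompt notification is required in situations other than those defined for SAEs above", and that this may cover "any event that the investigator regards as serious that did not strictly meet the criteria above but may have jeopardized the subject", events that needed intervention to prevent a listed outcome, and events that suggest a hazard, contraindication, side effect or precaution. It sets no deadline.

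Two firm rules are written for SAEs:

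- The same section requires every SAE to be reported, with the forms emailed within 24 hours.
- Protocol 7.5.1.2 halts the study on "The occurrence of any SAE considered at least possibly related to study agent administration in any 1 subject who received study agent".

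The other dosing criterion in 7.5.1.2 needs 30% of subjects within a dose level and covers listed toxicities only. One of these is "mild, moderate, or severe clinically significant anaphylactic reaction".

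The SAP has no SAE definition of its own. SAP 5.3.1 tabulates serious TEAEs.

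**The concern.** The Protocol introduces this as a first-in-human trial: "NH002 appears to have an acceptable safety profile to support the first-in-human study" (5.2.1). It also expects that reactions may be treated on site, since "necessary rescue material, equipment, and appropriate medications will be available in the clinic to allow rapid intervention in case of emergency" (7.5.1.6). Section 9.1.2.2.2 warns of serious cardiopulmonary reactions to perflutren microspheres, typically within 30 minutes. That is well inside the 4-hour observation period.

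A reaction that is treated promptly and resolves in the clinic can miss all five outcomes, even though it needed rescue treatment. It is also the kind of event that a one-subject rule should catch. On the text, two investigators could reasonably handle the same event differently. One would report within 24 hours and stop dosing; the other would record an ordinary AE. The trial is multicentre, so a missing deadline also affects how soon the sponsor and the other sites learn of the event.

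**Working it through.** The documents give no figure for this point (Protocol 10.8 states that no formal sample size calculation was required). The check is therefore a reading of the rules, followed by a count.

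**1. Can such an event miss the SAE list?** Take a reaction that is possibly related, treated in the clinic and resolved, with no admission and no immediate risk of death. It is not a death, disability or congenital anomaly. It is not a hospitalisation. It is not life-threatening, because the definition excludes reactions that could have been fatal only in a worse form. It meets none of the five outcomes.

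**2. Which rules then apply within a cohort?**

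| Rule | Trigger | Deadline for reporting | Stops dosing |
|---|---|---|---|
| SAE report, 9.1.2.2.1 | Defined SAE | 24 hours | No |
| One-subject criterion, 7.5.1.2 | Defined SAE, at least possibly related | – | Yes |
| 30% criterion, 7.5.1.2 | Listed toxicities only | – | Yes |
| Judgement paragraph, 9.1.2.2.1 | Judgement | None stated | No |
| Serious/not serious field, 9.1.2.2 | Investigator's classification | 24 hours if treated as an SAE | Yes if treated as an SAE and at least possibly related |
| General halt, 9.1.2.1 | Any safety concern | None stated | Yes |
| Report to study monitor, 9.1.2.2.1 | Event of major clinical concern, after dosing, linked to the study | None stated | No |

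The first two rules do not reach the event on the text. The last four depend on someone's judgement. The condition in the Synopsis for enrolling each ascending cohort controls the opening of the next cohort, not dosing within one, and no cohort follows Cohort 3.

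**3. Worst-case count.** Inputs: 12 subjects per cohort (Protocol 7.5.1.1), and scheduled DEC reviews after the first and the last subject (9.2). Assumptions: subjects are dosed one after another, no judgement-based route is used, and the Charter adds no review.

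- An event in subject k (k = 2 to 12) leaves 12 − k subjects who could be dosed before the next scheduled review. The maximum is 12 − 2 = **10**.
- For a listed toxicity, with the 30% taken over subjects dosed so far: 1/2 = 50% and 1/3 = 33.3% reach the criterion, but 1/4 = 25% does not. The first k that escapes is 4, so the maximum is 12 − 4 = **8**.
- With a denominator of 12: 0.30 × 12 = 3.6, so 4 events are needed. One event is 1/12 = 8.3%, and the maximum stays at **10**. The Protocol does not say which denominator applies.
- Under the one-subject criterion the count is **0** until the review.

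**4. How differently the two triggers behave.** The event rate p is assumed, since the documents give none. With n = 12, P(at least 1) = 1 − (1 − p)^12, and P(at least 4) is the binomial upper tail.

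| Assumed p | At least 1 of 12 | At least 4 of 12 |
|---|---|---|
| 2% | 21.5% | 0.01% |
| 5% | 46.0% | 0.2% |
| 10% | 71.8% | 2.6% |

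The last column matters only for toxicities listed in 7.5.1.2. The finding does not depend on these probabilities.

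**The case against.** The strongest reply is that the gap would rarely open in practice. The paragraph sits under the heading for the SAE definition and speaks of events that the investigator regards as serious. Section 9.1.2.2 makes every AE either serious or not serious, so an investigator who thinks an event serious will probably mark it so, and both firm rules would then follow. Section 9.1.2.1 words the halt for any safety concern as something that will happen, and a possibly related event needing rescue is hard to describe as no concern. The report to the study monitor adds a further route. An anaphylactic reaction with immediate risk of death is already an SAE. The milder ones fall under the 30% threshold, which is a separate question.

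Most of this stands, and it limits the point. It does not remove it: the same paragraph sets these events apart from defined SAEs, no route in the reply carries an express deadline for them, and their use can vary between investigators.

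A reader might infer three stronger things that the documents do not support:

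- That nothing would stop dosing after such an event. Sections 9.1.2.1 and 9.1.2.2 provide routes that may.
- That 10 further subjects would be exposed. That figure needs an event in subject 2 and the failure of every judgement-based route.
- That the events would disappear from the results. They remain in the general TEAE tables and in Listing 07, and are absent from the serious TEAE tables only if not marked serious.

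**Conclusion.** The point holds as a defect of wording with a safety consequence. For a single possibly related event that may have jeopardised the subject, or that needed intervention, the Protocol expressly requires neither the 24-hour report nor the one-subject halt. What is missing is a specific trigger and deadline that every site would apply in the same way.

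The size is bounded, not estimated: at most 10 further subjects per cohort, or 8 for a listed toxicity if the 30% is taken over subjects dosed so far, against 0 under the one-subject criterion. These limits rest on the assumptions stated with the count. The DEC Charter is not among the documents and may provide for other reviews. Confidence is medium. The change is worth making because it is small and the trial is a first-in-human dose escalation.

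**What to change.** Add a sixth criterion to the SAE list in Protocol 9.1.2.2.1, for example: *Is an event that, in the investigator's judgement, may have put the subject in jeopardy or needed intervention to avert any of the outcomes above.* Keep the word *may*, so that possible jeopardy stays covered.

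Such an event is then classified as serious, reported within 24 hours and included in the serious TEAE tables. If at least possibly related, it counts for the one-subject criterion in 7.5.1.2. Leave the existing judgement sentence in place for any other event, including those that suggest a significant hazard, contraindication, side effect or precaution.

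Whether an event fits remains the investigator's judgement; what follows from it becomes mandatory. The stopping rule is already written in terms of SAEs in the Synopsis, 7.1, 7.5.1.2 and SAP 1.2, so those texts need no change, and no new SAP table is needed. The CRF and SAE form are not among the documents, so their wording should be checked against the new criterion. The cost is an occasional extra halt and DEC review, and slightly more events shown as serious.
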